### **Surgical treatment for MMD**

Revascularization surgery has played an important role for treatment of MMD. Several general methods of revascularization had been used: direct, indirect and combined techniques. Two large studies with long term follow-up showed a good safety profile for surgical treatment. During the postoperative 30 days the risk of stroke is highest (approximately 4% per hemisphere); and after the first month, the risk decreases fairly. It is reported that patients have a 96% probability of remaining stroke-free over the subsequent 5 years. Patients with MMD have a higher risk of perioperative ischemic events. The complications associated with the treatment include stroke, infection, and intracranial hemorrhage.

Currently, there are no reports on the MMD research that refer to the criteria of receptor vessel selection in bypass surgery for MMD. Surgeons usually performed superficial temporal artery to MCA (STA–MCA) anastomosis. Sometimes when patients have severe ischemia in ACA area the STA can also be anastomosed to the branch of the ACA. So precisely choosing receptor vessel remains uncertain. As the imaging advanced, ASL can be used as a perfusion method to detect the ischemia area and intraoperative ICG angiography using Flow800 software can be used to reflect the lower flow velocity and superficial perfusion. Guided by this two imaging data, we try to precisely find the receptor vessel.

## **4. Primary Aim and Hypothesis**

### **Primary Aim**

To determine whether direct bypass surgery guided by multimodal neuronavigation is superior to empirical direct bypass procedure alone for preventing the primary endpoint (All strokes & death within 30 days post-surgery and ipsilateral hemorrhage afterwards) after cerebral revascularization surgery in ischemic MMD patients.

\*patients with TIA, stroke or other ischemic symptoms prior to enrollment that is attributed to progressive stenosis or occlusion in the terminal portion of the internal carotid artery and/or the initial portion of the anterior or middle cerebral arteries unilaterally or bilaterally and formation of abnormal collateral networks (moyamoya vessels) at the base of the brain.

### **Primary Hypothesis**

As compared with empirical direct bypass procedure alone, direct bypass surgery guided by multimodal neuronavigation will decrease the risk of the primary endpoint over 12 months in patients with MMD.

## **5. Study Plan and Procedure**

### **Study Design and Flow Chart**

This will be an investigator-initiated and **Phase III single center trial** in which patients with TIA, stroke or other ischemic symptoms prior to enrollment that is attributed to progressive stenosis or occlusion in the terminal portion of the internal carotid artery and/or the initial portion of the anterior or middle cerebral arteries unilaterally or bilaterally and formation of abnormal collateral networks (moyamoya vessels) at the base of the brain will be randomized (1:1) to:

Direct bypass surgery guided by multimodal neuronavigation. Combine local cerebral blood flow velocity and superficial perfusion assessed by Flow800 software that implements conventional ICG fluorescence angiography and deep perfusion assessed by multimodal MR (structure combined with perfusion sequence) to determine the recipient vessel.

OR

Empirical direct bypass surgery.

The evidence-based program of risk factor management will be administered to all patients by the study neurosurgeon at each site at regularly scheduled times throughout the study.

## **6. Study Endpoints**

### **6.1. Primary Endpoint**

All strokes & death within 30 days post-surgery and ipsilateral hemorrhage afterwards

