### **6.2. Clinical Secondary Endpoint**

- All kinds of adverse events related to surgery within 30 days
- Infarctions on the contralateral side within 1 year of randomization
- Transient ischemic attack on the surgically treated side within 1 year of randomization

- The changes from baseline in CBF measured by ASL at 7 days, 3 months, 6 months, 12 months or end of trial
- The changes from baseline in modified Rankin Scale (mRS) at 7 days, 3 months, 6 months, 12 months or end of trial
- The changes from baseline in National Institute of Health Stroke Scale (NIHSS) at 7 days, 3 months, 6 months, 12 months end of trial
- The changes from baseline in modified Barthel Scale at 7 days, 3 months, 6 months, 12 months or end of trial

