### **21.2. Description of analysis sets**

All patients who have been randomized to study treatment will be included irrespective of their protocol adherence and continued participation in the study. Patients will be analyzed based on the initial treatment assignment irrespective of whether the event occurred before or following discontinuation of study medication. Patients who withdraw consent to participate in the study will be included up to the date of their study termination except for vital status known through public records (for use in the analysis of all cause death). All efficacy variables will be analyzed using the full analysis set (FAS).

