## 21.7. Interim analyses

One interim analysis will be planned and conducted by the Data Monitoring Committee following the accrual and confirmation by adjudication of 50% of planned primary events. The stopping rule of Lan-DeMets approach to O'Brien-Fleming will be adopted for stopping for efficacy or futility. The efficacy stopping boundary at the interim analysis is a 2-sided p-value <0.0015 for the primary endpoint (one-year stroke or death). The final last level of significance with one interim analysis will therefore be 0.0489, with the family wise error rate controlled at 5.00%. The trial would be halted due to futility if nominal critical point (Standardized Z scale) for the primary endpoint crosses the internal boundary for futility ( $\pm 0.595$ ). It will be determined by the executive committee that the trial will be continued or stopped due to the overwhelming efficacy or futility after recommendation of Data Safety Monitoring Board.

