## 21.8. Censoring

Patients who have not had the event(s) in question will be censored at the earliest of EoT visit and the last study contact when all components of the endpoint in question were assessed. Lost patients in whom we cannot accurately determine if the primary endpoint occurred will be censored at the last contact date at which the patient was known to be free from a primary endpoint.

If the study is stopped early at the interim analysis, the mentioned-above censoring rule will apply. When the trial is determined to be stopped, all patients who have not completed the treatment period will be required for a EoT visit as soon as possible.

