
Other symptomatic intracranial hemorrhage
	
Any extravascular blood within the cranium associated with clinical deterioration, as defined by an increase of 4 points or more in the score on the NIHSS, or that led to death and that was identified as the predominant cause of the neurologic

	deterioration. Other Intracranial Hemorrhage is defined as an acute extravasation of blood into the subarachnoid space, epidural space, or subdural space with associated symptoms. Criteria: evidence of hemorrhage in the subarachnoid space, epidural space, or subdural space demonstrated by head imaging, surgery, or autopsy
Other Asymptomatic intracranial hemorrhage	An acute extravasation of blood into the subarachnoid space, epidural space, or subdural space without associated symptoms. Criteria: evidence of hemorrhage in the subarachnoid space, epidural space, or subdural space demonstrated by head imaging, surgery, or autopsy
Ischemic vascular death	Death due to ischemic stroke, myocardial infarction, sudden cardiac death, arrhythmia, pulmonary embolism, bowel or limb infarction, or any death not readily attributable to a non-ischemic cause
Hemorrhagic Vascular death	Death due to intracranial or systemic hemorrhage

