**modified Rankin Scale**

The modified Rankin Scale (mRS) is a scale commonly used for measuring the degree of disability or dependence in the daily activities of individuals who have suffered a stroke, and it has become the most widely used clinical outcome measure for stroke clinical trials.

Description	Score (select one)
No symptoms at all	0 
No significant disability despite symptoms; able to carry out all usual duties and activities	1 
Slight disability; unable to carry out all previous activities, but able to look after own affairs without assistance	2 
Moderate disability; requiring some help, but able to walk without assistance	3 
Moderately severe disability; unable to walk without assistance and unable to attend to own bodily needs without assistance	4 
Severe disability; bedridden, incontinent and requiring constant nursing care and attention	5 

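### A death after day 30 that is not due to ipsilateral hemorrhage enters no listed endpoint, and the protocol's sections disagree on whether late death counts

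*Protocol*

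**What the plan says.** The synopsis, section 4 and section 6.1 of the protocol give the same primary endpoint: "All strokes & death within 30 days post-surgery and ipsilateral hemorrhage afterwards". The Primary Hypothesis in section 4 says that navigation-guided bypass "will decrease the risk of the primary endpoint over 12 months in patients with MMD".

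Section 6.2 lists seven secondary endpoints. Three are events: "All kinds of adverse events related to surgery within 30 days", contralateral infarction, and TIA on the operated side. The other four are changes in CBF, mRS, NIHSS and Barthel score. The mRS form in the appendix ends at grade 5, "Severe disability; bedridden, incontinent and requiring constant nursing care and attention", and has no grade for death.

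On censoring, section 21.8 says: "Patients who have not had the event(s) in question will be censored at the earliest of EoT visit and the last study contact" at which all components of the endpoint were assessed. It gives no separate rule for death. Section 21.3 specifies a Cox model with treatment as the factor, and Kaplan-Meier event rates at the end of the trial.

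Three other places bear on death:
- Section 21.7 sets the interim efficacy boundary at a "2-sided p-value <0.0015 for the primary endpoint (one-year stroke or death").
- Section 21.2 includes patients who withdraw consent only up to study termination, "except for vital status known through public records (for use in the analysis of all cause death").
- The appendix on endpoint definitions defines ischemic vascular death and hemorrhagic vascular death, the latter as "Death due to intracranial or systemic hemorrhage". It ties neither to an endpoint.

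**The concern.** Take a patient who dies on day 60 of an infarct on the operated side. Section 6.1 does not count it: the 30-day window has closed and the cause is not a hemorrhage. Section 6.2 does not count it either. The adverse-event endpoint has ended, the infarct is not contralateral, the event is not a TIA, and the mRS form cannot record death. Under 21.8 the patient is censored.

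A reader of a 12-month surgical trial will want to know whether mortality differed between arms, and no listed endpoint answers that. Deaths also remove patients from the later mRS, NIHSS and Barthel comparisons, so those scales do not fill the gap.

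The conflict with 21.7 makes it worse. If the interim look counts strokes and deaths over a year and the final analysis uses 6.1, the two looks test different endpoints. The overall 5% error rate claimed in 21.7 presupposes the same endpoint at both.

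**Working it through.** **Step 1. Where does a death after day 30 go?**

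| Cause of late death | Section 6.1 | Section 6.2 |
|---|---|---|
| Ipsilateral hemorrhage | counted, through the hemorrhage | not needed |
| Contralateral infarct | not counted | the infarct counts, the death does not |
| Ipsilateral infarct | not counted | not counted |
| Contralateral hemorrhage, cardiac, other | not counted | not counted |

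Under the wording of 21.7, every row would be a primary event if it fell within one year.

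**Step 2. How far does the primary analysis respond to late deaths?** The protocol gives no late-death rate and says that the sample size was not derived from a formula, so there is no figure to reproduce. The inputs below are therefore assumed, apart from 50 per arm (section 21.1). Each arm has 2 primary events by day 30 and 1 ipsilateral hemorrhage at about day 200. Late deaths without ipsilateral hemorrhage number 0 in one arm and k in the other, spread over days 60 to 180. Everyone else is followed to day 365.

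| k against 0 | Cox HR as written (late deaths censored) | Cox HR counting death at any time | Fisher test of late deaths |
|---|---|---|---|
| 2 | 1.01 (p = 0.99) | 1.68 (p = 0.48) | p = 0.49 |
| 5 | 1.03 (p = 0.97) | 2.76 (p = 0.13) | p = 0.056 |
| 8 | 1.06 (p = 0.95) | 3.93 (p = 0.036) | p = 0.006 |
| 10 | 1.07 (p = 0.93) | 4.75 (p = 0.015) | p = 0.001 |

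The hazard ratio as written barely moves, because the deaths only shrink the risk set slightly.

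**Step 3. How biased is Kaplan-Meier as an absolute risk?** In the arm with deaths, two early events leave a survival of 48/50 = 0.96. At the late hemorrhage, 48 − k patients are at risk, so the Kaplan-Meier event rate is 1 − 0.96 × (1 − 1/(48 − k)). The cumulative incidence with death as a competing event is 3/50 = 6.0% for every k, because no one is lost for another reason.

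- k = 0: 1 − 0.96 × 47/48 = 6.0%
- k = 3: 1 − 0.96 × 44/45 = 6.1%
- k = 5: 1 − 0.96 × 42/43 = 6.2%
- k = 10: 1 − 0.96 × 37/38 = 6.5%

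The excess is about 0.1, 0.2 and 0.5 percentage points for 3, 5 and 10 deaths. It is upward, in the arm with more deaths.

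**Step 4. What could a mortality endpoint show at plausible counts?** One death is 1/50 = 2 percentage points of an arm. For 3/50 (6%) against 0/50, the two-sided Fisher p is 2 × (50 × 49 × 48)/(100 × 99 × 98) = 0.24.

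**The case against.** A reader might infer that an excess of late deaths would be invisible. The documents do not support that. Death is a serious adverse event in any study phase (section 18), adverse events and endpoints are collected at every visit after randomization (visit schedule), and the data safety monitoring board reviews the safety of both arms about every three months and may recommend stopping (section 22). An excess could be seen there. What these routes do not give is a named 12-month comparison in the trial's results.

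A reader might also infer that no analysis of all-cause death is planned. Section 21.2 mentions one, and section 21 leaves full detail to an SAP that is not shown. This stands as far as methods go: a competing-risk rule may be in the SAP. The list of endpoints, however, belongs to the protocol, and 6.2 omits mortality.

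A third tempting reading is that censoring makes the primary test invalid, as if the dead could still bleed. Censoring takes the patient out of the risk set, and the Cox model then estimates a cause-specific hazard ratio, which is a valid target. Only reading the Kaplan-Meier curve as absolute risk is biased, by little at these counts and not in favor of the arm with more deaths.

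It can also be said that the vascular-death definitions may serve to classify the 30-day deaths in 6.1, so they do not prove that an endpoint was lost. That is fair. Finally, entry requires mRS 0-2 and excludes a life expectancy under one year, so few late deaths are likely. That limits the size of the point, but leaves the contradiction between 6.1 and 21.7 untouched.

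**Conclusion.** The point holds in a limited form. Under 6.1, 6.2 and 21.8, a death after day 30 that is not due to ipsilateral hemorrhage is censored and counted as a death in no listed endpoint, although the hypothesis covers 12 months. The protocol also contradicts itself: 21.7 would count such deaths as primary events, and 21.2 refers to an analysis without a matching endpoint.

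The hole in the endpoint list and the two primary definitions are the substance. The statistical bias is minor: 0.2 to 0.5 percentage points in the Kaplan-Meier rate for 5 to 10 deaths in one arm. These sizes rest on assumed counts; the documents give no late-death rate. The two gaps in the text rest on no assumption. The sponsor should correct this, but it does not by itself undermine the primary test.

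**What to change.** 1. Reconcile 21.7 with 6.1, so that one primary definition applies at the interim and the final analysis.
2. Add all-cause death to 12 months to 6.2, and classify deaths by the two vascular-death definitions in the appendix, with the remainder as other.
3. State that vital status is sought to 12 months for every patient, including after a non-fatal primary event. Section 16 follows patients until the primary endpoint or the end of the trial, which can be read as ending follow-up at the first event. The public-record provision in 21.2 covers only withdrawn consent.
4. Keep the cause-specific Cox model and say that death without a prior primary event is censored in it. Report event rates as cumulative incidence with death as a competing event, in place of Kaplan-Meier.

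The cost is mainly wording, since deaths are already collected as serious adverse events, plus a 12-month vital-status check for patients who have had a primary event. The downside is one more secondary endpoint with low power: even 3 deaths against 0 gives p = 0.24. It should be reported as counts and a difference with a confidence interval, and non-significance should not be read as evidence of equal mortality.

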### **6.2. Clinical Secondary Endpoint**

- All kinds of adverse events related to surgery within 30 days
- Infarctions on the contralateral side within 1 year of randomization
- Transient ischemic attack on the surgically treated side within 1 year of randomization

- The changes from baseline in CBF measured by ASL at 7 days, 3 months, 6 months, 12 months or end of trial
- The changes from baseline in modified Rankin Scale (mRS) at 7 days, 3 months, 6 months, 12 months or end of trial
- The changes from baseline in National Institute of Health Stroke Scale (NIHSS) at 7 days, 3 months, 6 months, 12 months end of trial
- The changes from baseline in modified Barthel Scale at 7 days, 3 months, 6 months, 12 months or end of trial

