## 10. Randomization of Patients

The central randomized method based on our own system. Patient who has signed the informed consent form and met all inclusion criteria without any exclusion item could be enrolled. Once the patient enrolled in the study, the system will automatically assign the study patient a random number with the exact group that he/she should be treated. Then the investigator should record this number and group in the original case history and the coming treatment record of the study patient. According to the protocol, this patient should be treated into the randomized group or the control group.

The investigator's team should archive the randomized list and the related documents (randomized application form) together in the trial folder, which clinical trial department of the site has to store.

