## 18. Evaluation of End Points and Adverse Events

- **Adverse Event (AE):** An adverse event is the development of an undesirable medical condition or the deterioration of a pre-existing medical condition following or during exposure to a pharmaceutical product or device, whether or not considered causally related to the product. An undesirable medical condition can be symptoms (eg, nausea, chest pain), signs (eg, tachycardia, enlarged liver) or the abnormal results of an investigation (eg, laboratory findings, electrocardiogram). In clinical studies, an AE can include an undesirable medical condition occurring at any time, including run-in or washout periods, even if no study treatment has been administered.
- **Serious Adverse Event (SAE):** A serious adverse event is an AE occurring during any study phase that fulfils one or more of the following criteria:
  - i. Results in death,
  - ii. Is life-threatening,
  - iii. Requires inpatient hospitalization or prolongation of existing hospitalization,
  - iv. Results in persistent or significant disability/incapacity or substantial disruption of the ability to conduct normal life functions,
  - v. Is an important medical event that may jeopardize the patient or may require medical intervention to prevent one of the outcomes listed above.
- **Unanticipated Adverse Device Effect (UADE):** Any serious adverse effect on health

or safety or any life-threatening problem or death caused by or associated with a device, if that effect, problem or death was not previously identified in nature, severity or degree of incidence in the investigational plan or IDE application (including a supplementary plan or application), or any other unanticipated serious problem associated with a device that related to the rights, safety or welfare of subjects.

The following events have been identified as possible complications of revascularization surgery and are considered anticipated:

Vasospasm	Surgical Intervention	Arrhythmia
Vessel dissection	Neurological symptoms	Cardiac ischemia
Vessel occlusion	Pain	Coagulopathy
Vessel perforation	Pseudoaneurysm	Death
Vessel rupture	Renal insufficiency / failure	Emboli (air, tissue, thrombus or foreign body)
Vessel thrombosis	Respiratory Distress / failure	Hematoma, pain, and/or infection at access site
Stroke	Seizure	Hemorrhage
Transient ischemic attack	Infection	Hypertension
Syncope	Drug reaction to antiplatelet medication	Hypotension

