## 19. Core Lab

The core lab for imaging assessment is located at Peking University International Hospital. The Digital Imaging and Communications in Medicine (DICOM) imaging data will be collected, transported, and stored according to standardized protocol developed by lab committee. Imaging for diagnosis of MMD, hypoperfusion in the territory of culprit artery, event adjudication will be reviewed by specialists with experience in MR and angiography who are blinded to demographic and clinical characteristics and treatment assignment.

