### **21.3. Statistical Analyses**

All analyses will be based on the intent-to-treat principle using the FAS, including only events adjudicated by the Clinical Events Adjudication Committee (CEC). The primary hypothesis will be tested using a Cox proportional hazards model with a factor for the treatment group. The time to the first event was used in the model when there were multiple events of the same type. P values and Confidence Intervals (CI) for the Hazard Ratio will be obtained according to the Wald statistic. The following statistics, in addition to HR with CI will be also presented in the summary tables of these analyses: the number of patients with event and Kaplan-Meier estimates of the event rate per treatment group calculated at EoT. Kaplan-Meier estimates of the cumulative proportion of patients with primary endpoint events will be calculated and plotted.

The potential impact of loss to follow-up will be evaluated by the sensitivity analysis.

A Cox proportional hazards model will be used to assess differences between study groups in the rate of primary endpoint under the following three scenarios: (1) all patients will be thought to experience primary endpoint event when the final disposition for the event adjudication is not determined. (2) only patients in the empirical bypass arm will be thought to experience primary endpoint event when the final disposition for the event adjudication is not determined. (3) only patients in the multimodal neuronavigation guiding bypass arm will be thought to experience primary endpoint event when the final disposition for the event adjudication is not determined. These results under the three scenarios will be compared with the result under the scenario in which all patients will be not thought to have primary endpoint event when the final disposition for the event adjudication is not determined. However, the primary analysis result will be reported in patients who are censored not to have the event occurrence when the final disposition for the event adjudication is not determined.

The analysis of and the secondary efficacy variable for the test of multimodal neuronavigation guiding bypass against empirical bypass will comprise the confirmatory analysis. No multiplicity adjustment will be made in all analysis including a confirmatory testing (subgroup analysis).

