#### **21.4. Clinical Site Effect**

All revascularization surgeries will be performed by the same experienced neurosurgeon.

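### The 30-day adverse event endpoint counts only surgery-related events, with no stated assessor or masking of that judgement; comparing all events by arm would make the judgement unnecessary

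*Protocol*

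**What the plan says.** The first item in the list of secondary endpoints, worded identically in the synopsis and Section 6.2, is "All kinds of adverse events related to surgery within 30 days". The restriction to related events is therefore a deliberate part of the endpoint definition.

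Other parts of the protocol bear on it:

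- **Section 18** defines an adverse event broadly, "whether or not considered causally related to the product". The visit schedule in the appendix has adverse events recorded at discharge and at every later visit.
- **Section 18** also lists surgical complications under the sentence "The following events have been identified as possible complications of revascularization surgery and are considered anticipated". The list is not tied to the Section 6.2 endpoint.
- **Section 5** gives the control arm as "Empirical direct bypass surgery", so both arms have a direct bypass.
- **Section 21.4** states "All revascularization surgeries will be performed by the same experienced neurosurgeon".
- **Section 10**, on allocation: "Then the investigator should record this number and group in the original case history".
- **Section 19** has imaging, including imaging for event adjudication, reviewed by specialists "blinded to demographic and clinical characteristics and treatment assignment".
- **Section 21.3** restricts all analyses to events adjudicated by the Clinical Events Adjudication Committee (CEC) and makes no multiplicity adjustment.
- **Section 6.1** counts all strokes and deaths in the first 30 days in the primary endpoint, with no causality condition.

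**The concern.** A relatedness filter is a judgement made event by event after the operation. It can differ between arms when the person judging knows which technique was used and has a view about it. The surgeon necessarily knows the technique, and the investigator writes down the group. If events after the guided procedure were less readily attributed to surgery than events after the empirical one, the endpoint would show a safety advantage that does not exist. Attribution differing the other way round, or set against a real difference, could conceal one.

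The filter is also unnecessary for the comparison. Every patient is planned to have a bypass by the same operator, and randomization balances events unrelated to the operation in expectation. A count of all events is a fair comparison as it stands.

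The boundary of the filter is unclear as well. Section 12 adds fluorescence angiography and electromagnetic navigation to the guided procedure. Whether an event arising from those steps counts as surgery-related is left open, and such events would fall on one arm only if control operations do not use them.

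**Working it through.** **1. Does a stated safeguard reach the relatedness judgement?**

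- *Masked imaging review (Section 19).* It covers events judged on images. The Section 18 list includes infection, seizure, renal failure, respiratory distress and drug reaction, which are not in general settled by an image.
- *Adjudication packet (Section 17).* It is described for potential neurological events and is prepared by the site.
- *CEC rule (Section 21.3).* It applies to all analyses, but does not say that the committee is masked or that it rules on relatedness.
- *Primary endpoint (Section 6.1).* It takes in all 30-day strokes and deaths, so these do not depend on attribution.

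The exposure is therefore confined to this secondary endpoint, chiefly its non-neurological, non-imaging events.

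**2. How large could the effect be?**

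The protocol has no figure to reproduce: it gives no adverse event rate or attribution rate, and Section 21.1 says the sample size does not come from a formula. From the protocol: 100 patients, 1:1, so n = 50 per arm. Assumed: true event rates, attribution probabilities and a two-sided 5% level.

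Observed rate in an arm = true rate × probability of being called related.

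For counts i and j, z = (|i − j|/50) / √(p̄(1 − p̄)·2/50), with p̄ = (i + j)/100. The rejection probability is the sum of Bin(i; 50, p₁) × Bin(j; 50, p₂) over all pairs (i, j) that the test rejects. Fisher's exact test was evaluated in the same way.

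*Creating a difference* (same true rate in both arms). Each cell gives z test / Fisher rejection probability:

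| True rate | Attribution 80% v 80% | 70% v 90% | 50% v 90% |
|---|---|---|---|
| 10% | 4.7% / 1.5% | 6.1% / 2.1% | 11.0% / 4.3% |
| 20% | 5.5% / 2.5% | 9.0% / 4.7% | 22.1% / 12.9% |
| 30% | 5.1% / 3.0% | 10.9% / 7.2% | 31.8% / 23.8% |
| 40% | 4.9% / 3.0% | 13.5% / 9.6% | 43.4% / 35.4% |
| 60% | 5.7% / 3.5% | 24.2% / 18.3% | 70.2% / 62.6% |

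Example: at a true 40%, attribution of 70% v 90% turns 40% v 40% into 28% v 36%.

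*Hiding a difference:*

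- True 20% v 40%, all events counted: power 59.5% (z), 51.5% (Fisher).
- The same with attribution 90% v 60%: observed 0.20 × 0.90 = 18% v 0.40 × 0.60 = 24%; power 11.6% (z), 7.4% (Fisher).
- True 15% v 30%: power falls from 44.3% to 10.1% (z) and from 35.4% to 5.3% (Fisher) under the same attribution.

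**3. What a single trial might look like.** Suppose 20 of 50 patients in each arm have an event, with 60% called related in the empirical arm and 40% in the guided arm. The endpoint shows 20 × 0.60 = 12 against 20 × 0.40 = 8, a relative risk of 8/12 = 0.67. Then p̄ = 0.20, the standard error is √(0.20 × 0.80 × 2/50) = 0.08, and z = 0.08/0.08 = 1.0. Even a 20-point gap in attribution need not give a significant result.

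**The case against.** A reader might infer that relatedness is judged by someone who knows the allocation. The documents do not say so. They name no assessor; knowledge of the arm is shown for the surgeon and the investigator, but neither is given the task. Section 16 assigns follow-up interviews to study neurologists, and Section 21.3 sends counted events to a committee. The risk is open, not demonstrated.

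A reader might also take this as the trial's main safety comparison. That goes too far. The gravest 30-day outcomes are in the primary endpoint without a filter, the monitoring board reviews safety in both arms about every three months (Section 22), and nothing prevents an all-event table. First place in the list carries no stated rank.

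Three further objections have weight:

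- Attribution criteria are commonly left to the analysis plan, which is not at hand. Their absence alone is no defect. The restriction itself, however, is fixed in the protocol's endpoint definition.
- The causality phrase in Section 18 concerns a drug or device product, not surgery. It still shows that an event need not be judged causal to be an adverse event.
- The complications list is broad. If applied as the rule, it would leave less room for the attribution gaps assumed above. But it is not linked to the endpoint, and entries such as pain and hypertension make it a poor test of cause.

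The case for choosing surgical complications as an outcome of interest also stands. It supports reporting that subset, but not making it the only comparison.

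**Conclusion.** The point holds in a limited form. The 30-day adverse event endpoint depends on a relatedness judgement that the comparison does not need, and no stated safeguard clearly masks that judgement for events outside neurology and imaging. Unequal attribution could move the result in either direction. Primary-endpoint strokes and deaths within 30 days are unaffected.

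The size is unknown. With a 20-point attribution gap (70% v 90%), the inflation is small when events are rare (6.1% by the z test at a true rate of 10%) and material when they are common (24.2% at 60%). Larger gaps do more. All of this rests on assumed rates and an assumed nominal 5% test. This is a cheap improvement to one secondary endpoint and no threat to the primary analysis.

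**What to change.** In Section 6.2 and the synopsis, define the by-arm comparison as all adverse events within 30 days after surgery, regardless of attribution, with serious events shown separately. Report the surgery-related subset as supportive, and say who makes that judgement and that they are masked to arm.

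One consequential clarification is needed in Section 21.3: state that this comparison is not limited to CEC-adjudicated events, or that all 30-day events go to the committee. Otherwise a filter could return by that route.

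The cost is a few lines of text. Section 18 already defines events broadly and the visit schedule already provides for recording them. Onset dates are needed, because in that schedule the first visit after discharge is at 3 months.

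There are two downsides. Unrelated events will dilute the contrast, probably slightly, though the protocol gives no background rate. The change also removes bias from attribution but not bias from unmasked reporting: staff who know the arm may still record events differently.
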